5.2.2. Fecal microbiota or placebo transplantation (8 weeks)

Approximately 48 hours after stopping antibiotics or placebo antibiotics, subjects will return for a clinic visit in the Clinical and Translational Study Unit (CTSU) for administration of either FMT or placebo. At the visit, they will undergo a medical exam by the investigator and laboratory samples will be collected. Subjects will then receive an induction retention enema of either FMT or placebo over a 15-30 minute period and will be encouraged to retain the inoculum for as long as possible. Subjects will be observed for 60 minutes after last enema and before discharge.

Subjects will return to the CTSU weekly, for a total of 7 weeks, for administration of blinded study treatment (FMT from the same donor or placebo). Prior to each weekly visit, subjects will provide stool and complete a survey (PUCAI) to monitor symptoms, medications and disease activity. At week 4 and week 8, subjects will also have routine laboratory assessments and a medical examination by the investigator. Adverse events will be assessed at each visit.

5.2.3. Open-label FMT or Follow-up

After completing 8 weeks of blinded study treatment, study subjects will be given the option to receive open-label maintenance FMT weekly for the remainder of the study if they initially received placebo and did not improve OR if they received FMT, improved, and wish to continue treatment. Subjects will be considered to have improved if their PUCAI score shows improvement of at least 10 points compared to baseline or a score of 10 points or less.

After a subject receives the last dose of blinded study treatment at week 8, the subject's treatment assignment will be unblinded to determine the appropriate course of action. Those subjects, who 1) are found to have improved after receiving 8 weeks of placebo or 2) are found not to have improved after receiving 8 weeks of FMT, will not be eligible to receive open-label FMT. Those subjects will be considered in follow up and will have disease status assessments conducted weekly for the 1st month and then monthly for the following month or 5 months. Subjects will also collect a stool sample and have medical examinations done at 3 and 6 months after their last dose of FMT.

Study subjects who are eligible and interested in continuing on to open-label FMT can be enrolled within 14 days (\pm 7 days) following blinded treatment completion. For the open label phase, subjects who received active treatment (FMT) will proceed directly to open label treatment weekly capsules. However, subjects randomized to placebo (aka no antibiotics, no FMT) will undergo a 7-day antibiotic conditioning and a 2-day rest period prior to commencing open-label FMT treatment that will begin with a retention enema. Thereafter, all subjects will return weekly for observed FMT administration as previously described, AE assessment and survey and stool collection. Routine laboratory assessments and medical exams will be conducted monthly. At all times during this study, standard of care progression of medical/surgical therapy will be offered if clinical course dictates it is necessary for both FMT and placebo arms of the study.

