3. STUDY DESIGN

3.1. Study Schema

Description

This is a single-center, phase I/II, randomized, prospective, double-blinded, placebocontrolled study of FMT in the treatment of active pediatric UC. The primary aim is to assess safety and feasibility of a weekly FMT maintenance therapy. A total of 60 patients with active UC (as defined by PUCAI score of > 9) will be enrolled and randomized to first receive FMT or placebo (study treatment).

For therapy/placebo induction, a retention enema will be administered according to the treatment arm to which the patient is assigned. FMT by retention enema will afford us the best delivery method equivalent to that previously described by Moayyeddi and Kunde (see Background) for engraftment of donor stool using FMT materials available to us. Subsequent administrations will occur as oral, frozen encapsulated inocula/placebo for 7 weeks. After the first 8 weeks, subjects will have the option to continue on study treatment or switch to open-label FMT. Subjects will be followed by telephone to assess adverse events for a total of 6 months after their last FMT dose.

Patient metadata and stool samples will be collected at key time points. The patient-reported metadata collection technique will allow for numerous clinical correlations to be parsed out using the random forest machine learning capabilities of synthetic learning in microbial ecology (SLiME) to identify taxonomic features associated with important clinical parameters.(22)

An initial subset of 10 subjects will be enrolled in the study (will be limited to only those patients 12 years of age or older and to those who have mild to moderate ulcerative colitis) and randomized to receive FMT or placebo. We'd expect short term adverse events to occur within 7 days of FMT administration. Individual subject safety data will be reviewed by the PI to assess whether FMT appears to be safe in the subject before continuing the subject towards open-label use of FMT.

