3.2.1. Inclusion Criteria

Male and female children and young adults, aged 5 years to 30 years, who meet the following inclusion criteria, will be enrolled in the study.

An initial subset of 10 subjects will be limited to patients with mild to moderate ulcerative colitis (i.e., PUCAI < 65) and to individuals ≥ 12 years of age. If FMT appears to be safe in this subset of patients after 8 weeks in the study (to be assessed by a Data Safety Monitoring Board), expanded enrollment as is described above will occur.

All patients must satisfy below criteria:

- 1. Have UC (PUCAI >9) and have failed, are intolerant to, or have refused first-line maintenance therapy.
- 2. Have had visual or histologic evidence of inflammation confirmed through colonoscopy ideally within 90 days but no more than 105 days prior to randomization.
- 3. Have negative test results for Hepatitis B (HBV), Hepatitis C (HCV), and Human Immunodeficiency Virus (HIV).
- 4. Have a negative urine hCG test if female of childbearing potential.
- 5. Able to swallow antibiotic, FMT or placebo capsules.
- 6. Able to give informed consent and/or assent as appropriate (patients 12-17 will be asked to provide written assent, patients 5-11 will be observed for assent or dissent behaviorally, or with verbal/written communication)
- 7. Willing and able to participate in the study requirements, including serial stool collection, survey completion and clinic visits.
- 8. Willing to undergo telephone follow-up to assess for safety and adverse events.
- 9. Must be free of any known food allergy.
- 10. Agrees and willing to have an enema for purposes of induction therapy.

Patients who have disease that has required other medications (including steroids, immunosuppressives, and biologics) will be included.

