3.2.2. Exclusion Criteria

Subjects who fall into any of the following exclusion criteria at the time of screening are not eligible for enrollment into the study.

- 1. Patients in a clinical remission (PUCAI \leq 9).
- 2. Patients with recent (within 4 weeks) dose change of biologics, 5-ASA, steroids or immunomodulators
- 3. Patients considered to have toxic megacolon.
- 4. Patients with a known drug allergy to vancomycin, metronidazole or polymyxin.
- 5. Patients with a history of aspiration, gastroparesis, surgery involving the upper gastrointestinal tract (that might affect upper gastrointestinal motility) or unable to swallow pills.
- 6. Patients with esophageal dysmotility or swallowing dysfunction.
- 7. Patients with known food allergies.
- 8. Patients with positive test results for HBV, HCV, or HIV.
- 9. Female patients with a positive test result on a urine hCG test.
- 10. Patients unwilling or unable to give consent or participate in all study requirements.
- 11. Patients unable or unwilling to receive a retention enema for purposes of induction therapy.

- 12. Patients with recent (within 6 weeks) systemic antibiotic use.
- 13. Patients who have testing consistent with active clostridium difficile.
- 14. Patients with known prior experience with donor FMT.

Research personnel and care providers will be educated about inclusion/exclusion criteria so that only appropriate patients are approached for informed consent. This will reduce the burden of worry for families and patients as to whether they are suitable candidates for the study. Subjects who are found to have no evidence of active disease by colonoscopy will be excluded from the study.

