5.1. Schedule of Events

SCREENING		BLINDED TREATMENT							OPEN-LABEL FMT						FO	OLLOW	Early Termination		
	Day	Day			Visit Week (± 2 days)			1	Day			Visit Week (± 2 days)			Month				
Procedures	-90 to -9	-8	-1	0 (Wk 1, D1)	2-3	4	5-7	8		-8	-1	0 (Wk 9, D1)	Weekly	Every 4 weeks	1,	2,4,5	3	EOS 6	
Informed Consent	х																		
Eligibility	х								Ş										
MD visit	х			х		х		х	Į DIL			x		х			х	х	
HBV, HCV, HIV ³	х								UNBLINDING										
Lavage	х								NN										
Colonoscopy (up to 105 days)	х																		
Randomization		x																	
Antibiotics ¹ /placebo		Х								\mathbf{X}^{11}									
hCG ³	х	X ⁸				x		x		X^8				х					
Labs ²	х			х		х		х	1			х		х			х	х	х
Disease activity surveys 5	х	х	х	х	х	х	х	х		х	х	х	x			x	х	х	х
Stool sample ^{7,9}		х		х	х	х	х	х		х		х	x				х	х	х
AE assessment by RN/MD		х	х	х	х	х	х	х		х	х	х	х	х		x ⁶	х	х	х
Telephone contact by RN/MD			x								x					х			
FMT/placebo dosing				X^4	х	х	х	х				X ^{4,10}	X ¹⁰						

¹7-day induction regimen of 3 antibiotics (vancomycin 125 mg, polymixin 62.5 mg, and metronidazole) BSA for vancomycin 125 mg, polymixin 62.5 mg = SQRT [(cm*kg)/3600]

<0.5 m²: PO 1 capsule, TID

 $0.5 - 1 \text{ m}^2$: PO 2 capsules, TID

1-1.5 m²: PO 3 capsules, TID

1.5 -2 m²: PO 4 capsules, TID

Metronidazole weight-based dosing parameters

12.5 kg \geq Patient Weight > 25.0 kg: 125 mg PO BID 25.0 kg \geq Patient Weight > 37.5 kg: 250 mg PO BID 37.5 kg \geq Patient Weight > 50.0 kg: 375 mg PO BID Patient Weight \geq 50 kg: 500 mg PO BID

² "Screening labs" are considered for research purposes only, and will be covered by the study. Routine laboratory assessments are per routine clinical care, and if you are a patient at BCH, these will be

covered by the subject's insurance company. If the patient is not seen at BCH, then these are considered for research purposes and will be covered by the study.

³ HBV, HCV, HIV, and hCG testing are research-only labs and are required to be obtained no earlier than 2 weeks prior to the 1st FMT dose.

⁴ Initial FMT/placebo dose (Week 1 of blinded therapy will be administered as a retention enema). Week 1 of open label therapy will be a selective FMT induction enema or FMT weekly capsule.

⁵ Disease activity surveys include the Patient Reported Outcomes Diary and Pediatric Ulcerative Colitis Activity Index

⁶ Weekly telephone AE Assessments will also be conducted on a weekly basis for the 1st month of follow-up.

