0.5-1	2	3 times a day				
1-1.5	3	3 times a day				
1.5-2	4	3 times a day				

*BSA will be calculated as **BSA = SQRT [(cm*kg)/3600]**

2) A third antibiotic metronidazole administered orally (PO) as a separate capsule according to the following weight-based dosing parameters:

Patient Wt (kg)	Dose (mg)	Frequency			
12.5 - 25.0	125	2 times a day			
25.0 - 37.5	250	2 times a day			
37.5 - 50.0	375	2 times a day			
>50.0	500	2 times a day			

Corresponding placebo for each antibiotic will be supplied and distributed by the BCH Research Pharmacy.

Clinical data including symptom logs, medications and disease activity and stool samples will be collected at the time of study entry and after completion of the antibiotic regimen. Routine laboratory analysis will be done at the time of enrollment and before commencing study treatment.

Subjects who meet all eligibility criteria will be randomized to receive either FMT or placebo.

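### Section 5.2.3 classes a subject whose PUCAI is 10 at baseline and still 10 at Week 8 as improved, although nothing has changed

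*Combined protocol and SAP*

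**What the plan says.** Under section 5.2.3 of the combined protocol and SAP, treatment assignment is unblinded after the Week 8 dose. Open-label FMT is then offered to placebo subjects who did not improve and to FMT subjects who did. Improvement is defined on the PUCAI as "improvement of at least 10 points compared to baseline or a score of 10 points or less". Placebo subjects who "are found to have improved after receiving 8 weeks of placebo" cannot receive open-label FMT, and neither can FMT subjects who did not improve.

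Three other places fix the meaning of a score of 10:

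- Section 3.2.1 requires subjects to "Have UC (PUCAI >9) and have failed, are intolerant to, or have refused first-line maintenance therapy"; sections 3.1 and 3.2 use the same cut for active disease.
- Section 3.2.2 excludes patients in clinical remission, set at a PUCAI of 9 or less.
- Section 5.3.3 defines remission as a secondary outcome with the same cut of 9 or less.

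Section 4.1.3 describes the same decision in terms of response: subjects who responded to FMT, or who failed to respond to placebo, have the option of weekly open-label FMT.

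**The concern.** The two conditions in 5.2.3 are joined by *or*, and only the first refers to change. The second is met by the Week 8 score alone, and its cut of 10 overlaps by one point with the range that counts as active disease at entry. The same score of 10 is therefore active disease at screening, is not remission at Week 8, and is still labelled improved.

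The label controls access to treatment in both directions. An unchanged placebo subject with active disease is treated as a responder and refused open-label FMT. An unchanged FMT subject may continue weekly donor material, with the risks described in 4.1.5, without any gain on the PUCAI. Neither result fits the response wording of 4.1.3. No other section adds a requirement for a fall.

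**Working it through.** The plan gives no figure to reproduce here; the check is one of logic.

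**Inputs.** Let *b* be the baseline PUCAI and *w* the Week 8 PUCAI, both taken as whole numbers. That is an assumption, since the protocol does not give the point values of the index.

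- Eligible baseline: *b* > 9, so *b* ≥ 10 (3.1, 3.2, 3.2.1, 3.2.2).
- Remission: *w* ≤ 9 (3.2.2, 5.3.3).
- Improved, as written: *b* − *w* ≥ 10, or *w* ≤ 10 (5.2.3).

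**Step 1: the case 10 to 10.** The subject is eligible, because 10 > 9. The fall is 10 − 10 = 0, so the first condition fails (0 < 10). The second condition holds (10 ≤ 10). The subject is improved, yet not in remission (10 > 9).

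**Step 2: is it the only such case?** No fall means *w* ≥ *b*, so *b* − *w* ≤ 0 and the first condition always fails. The subject can then be improved only if *w* ≤ 10. Together with *b* ≥ 10 this gives 10 ≤ *b* ≤ *w* ≤ 10, hence *b* = *w* = 10. With an eligible baseline there is exactly one such pair, whatever the upper limit of the scale.

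**Step 3: routing of that subject under 5.2.3.**

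| Arm | Label as written | Open-label FMT | If labelled not improved |
|---|---|---|---|
| Placebo | Improved | Refused | Offered |
| FMT | Improved | Offered | Refused |

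**Step 4: the proposed rule.** Improved if *b* − *w* ≥ 10, or *w* ≤ 9, or (*w* = 10 and *w* < *b*). It can differ from the current rule only at *w* = 10. There the current rule always says improved, while the proposed rule says improved only if *b* > 10. With *b* ≥ 10, the only change is at *b* = 10. Any subject with *w* ≤ 9 remains improved whatever *b* is.

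**Step 5: a plain cut of 9 or less, for comparison.** At *w* = 10 a subject would then need *b* − 10 ≥ 10, that is *b* ≥ 20. Every eligible baseline from 10 to 19 that ends at 10 would change label, which reaches well beyond the case with no change.

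**The case against.** The strongest reply is that the absolute condition is a deliberate low-activity rule. A subject who enters at 10 could satisfy the 10-point fall only by reaching 0, so some absolute condition is needed at low baselines. Ten is also the lowest eligible whole-number score, and sparing such a placebo subject the antibiotics, enema and weekly FMT is a defensible clinical choice. This justifies having an absolute condition. It does not explain calling an unchanged score improved, and it does not cover the FMT arm, where the same label permits more FMT rather than less. The documents do not state this rationale.

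A second reply is that the case is marginal: open-label FMT is optional, and standard therapy stays available in both arms (sections 5 and 5.2.3). That stands, and it limits the weight of the point.

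A reader might also infer that the rule labels subjects who got worse as improved. Section 5.2.3 does not name the baseline visit, and PUCAI surveys are also scheduled on Day -8, Day -1 and Day 0 (5.1). Section 5.2.1 says that "disease activity and stool samples will be collected at the time of study entry and after completion of the antibiotic regimen". A Day 0 score could be 9 or less, and a rise from there to 10 would still meet the absolute condition. The documents do not support this as a finding. Section 7.3 uses baseline PUCAI to judge whether randomization balanced the groups, which suits a score taken before one arm has had antibiotics. Section 3.2.2 ties the remission exclusion to screening, and 3.2.3 allows withdrawal of a subject who no longer meets the entry criteria. None of these formally defines baseline, but they favour the reading in which only 10 to 10 is affected. Counting score pairs under the wider reading would also depend on a step size that the protocol does not give, and would say nothing about how many subjects are involved.

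**Conclusion.** The point holds, as a minor one. Read literally, 5.2.3 classes a subject at 10 on both occasions as improved, and in either arm this reverses the access to open-label FMT that an unchanged subject would otherwise have. With an eligible baseline and whole-number scores, it is the only pair without a fall that is affected. How many subjects would fall into it cannot be derived from the documents; the number is probably small.

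It would be a mistake to infer that the trial's results are distorted. The primary outcome concerns adverse events. The PUCAI secondary outcomes are remission at 9 or less and improvement of 20 points or more, and neither uses the 5.2.3 definition. The consequence is confined to who is offered open-label FMT after Week 8.

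**What to change.** In 5.2.3, keep the 10-point fall and replace the absolute condition with: *a score of 9 points or less, or a score of 10 points that is lower than baseline*.

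With an eligible baseline this relabels only the 10-to-10 subject. Every subject in remission at Week 8 stays improved, whichever pre-dose visit is taken as baseline. The change therefore does not require the screening score to be named as baseline. That would be a separate and debatable decision: screening runs from Day -90 to Day -9, and the choice would affect the 10-point condition for all subjects.

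The plain cut of 9 or less is not preferred. An FMT subject who fell from 15 to 10 would lose continuation, and a placebo subject with the same fall would become eligible for antibiotics, an enema and weekly FMT.

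One limit remains: if the scale allows it, a fall from 11 to 10 would still count as improved, as it does now. The cost is one phrase, with no change to sample size, visits or analyses.

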4.1.4. Blinding and Randomization

The first ten eligible subjects will be randomized in a 1:1 ratio according to a pre-determined block randomization procedure to receive either FMT or placebo. If safety allows, the remaining cohort of 50 eligible subjects will be randomized in a 1:1 ratio according to a pre-determined block randomization procedure to receive either FMT or placebo. An unblinded pharmacist or delegate will maintain the randomization list ensuring subjects are randomized appropriately and dispensed the correct treatment. The investigator, research personnel and study subjects will be blinded to treatment assignments.

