6. SAFETY ASSESSMENT

6.1. Adverse Event Assessment and Reporting

Comprehensive assessments of any apparent adverse event(s) (AE) experienced by the study subject will be performed throughout the course of the study.

The PI will submit reports of unexpected Serious adverse events (SAEs) and other unanticipated problems to the Institutional Review Board (IRB) at Boston Children's Hospital and to OpenBiome according to their policies.

The PI will report events that are both serious and unexpected and that are associated with FMT/study intervention to the FDA and other applicable health authorities within the required timelines as specified in 21 CFR 312.32 (IND Safety Reports).

The following unexpected AEs will be assessed, recorded and reported to the Data Safety Monitoring Board (DSMB) on an expedited basis: all SAEs, AEs grade 3 (according to CTCAE 5.0 (31) if applicable) or above, and any unexpected AEs grade 2 or above that is possibly or probably related to FMT (as determined by a blinded investigator). Only an AE that meets the above criteria will be recorded and reported. Each reported AE will be described by its duration (i.e., start and end dates), regulatory seriousness criteria if applicable, expectedness, suspected relationship to the study treatment, and actions taken (a blinded investigator will determine expectedness, severity and relationship to study treatment).

Individual subject participation will be temporarily halted until the DSMB determines appropriateness of re-initiation of therapy in any subject experiencing an adverse event resulting in: an Emergency Department visit that is possibly or probably related to FMT, significant worsening of their disease, or experiences 1 SAE Grade \geq 3.

Individual subject participation in the study will be permanently stopped if a SAE Grade ≥ 3 is deemed possibly or probably related to FMT, including any hospital admission.

If 2 or more subjects experience 1 SAE grade \geq 4, all study activities will be halted until the DSMB determines appropriateness of re-initiation of therapy in any subject.

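### The plan sets no minimum interval between the Week 8 dose and unblinding, so blinded judgement of adverse events in the following 7 days is not secured

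*Combined protocol and SAP*

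**What the plan says.** - **Unblinding (Section 5.2.3).** Once the last blinded dose has been given at Week 8, the subject's "treatment assignment will be unblinded to determine the appropriate course of action", that is, to decide between open-label FMT and follow-up. The section does not say how long after the dose this happens or who is told. Open-label entry is set at 14 (± 7) days after blinded treatment ends.
- **Schedule of Events (Section 5.1).** Dosing and AE assessment share the Week 8 visit. The unblinding column comes next, with no AE contact in between.
- **AE judgement (Section 6.1).** For each reported AE, "a blinded investigator will determine expectedness, severity and relationship to study treatment". The rule has no end date.
- **Who is blinded (Section 4.1.4).** "The investigator, research personnel and study subjects will be blinded to treatment assignments". No section names an AE assessor who stays blinded after Week 8.
- **Timing of events (Section 3.1).** "We'd expect short term adverse events to occur within 7 days of FMT administration".
- **Primary safety outcome.** Section 5.3.3 counts subjects with FMT-related events of grade 2 or above eight weeks after FMT, without saying which dose starts the clock. Sections 7.1 and 7.3 test new SAEs or worsening of existing AEs, which Section 7.1 counts over the study period after enrolment.

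**The concern.** The last blinded dose has the same expected 7-day event window as the other seven. The Week 8 visit can capture events from earlier doses, but most events from the Week 8 dose will first reach the team at a later contact. Nothing in the plan keeps that contact blinded.

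Both descriptions of the primary outcome are sensitive to this, in different ways:

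- **Section 5.3.3 outcome.** It depends on relatedness. Once a subject is known to have had placebo, an event is unlikely to be called FMT-related, whereas the same event in the FMT arm can be. Section 6.1 adds that an unexpected grade 2 event qualifies for recording and expedited reporting only if judged possibly or probably related, although Section 8 also keeps a running AE log.
- **Sections 7.1 and 7.3 outcome.** It needs no relatedness call, but whether an existing AE has worsened is a severity grade, and a grade given with knowledge of the arm can shift.

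Subjects who know their arm may also report symptoms differently.

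**Working it through.** The plan gives no figure to reproduce here. The check is a day count followed by a bound on the exposure.

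**1. Dose days.** Take Week 1 Day 1 as Day 0. One enema visit plus seven weekly capsule visits (Section 4.1.3) gives doses on Days 0, 7, 14, 21, 28, 35, 42 and 49. The Week 8 dose is Day 49.

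**2. Event window of the last dose.** Adding the 7 days of Section 3.1: 49 + 7 = 56, so Day 49 to Day 56.

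**3. Does that week count toward the primary outcome?**
- Eight weeks from the first dose: 0 + 56 = Day 56. The week is inside.
- Eight weeks from the last dose: 49 + 56 = Day 105. The week is inside.
- Study period after enrolment (Section 7.1): the week is inside.

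**4. Share of that week left unprotected.** If the assignment is released d days after the dose, the share is max(0, 7 − d)/7.

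| Release, days after Week 8 dose | Share of the 7-day window |
|---|---|
| 0 | 100% |
| 2 | 5/7 = 71% |
| 7 or more | 0% |

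**5. Share of the blinded phase.** One dose of eight: 1/8 = 12.5% of dose-weeks, at most.

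**6. Subjects involved.** Assume events are spread evenly over the eight dose windows, with 30 subjects per arm. At the 10% rate of Section 7.1: 30 × 0.10 / 8 = 0.375, about 0.4 per arm. At 15%: 30 × 0.15 / 8 = 0.5625, about 0.6 per arm. The documents do not give the true spread.

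**7. Sensitivity of the test.** Illustration: two one-sided tests with a Wald standard error, margin 0.20, and placebo fixed at 3/30. The larger p-value is that for z = (0.20 − |difference|)/SE.
- FMT 3/30: SE = √(2 × 0.10 × 0.90/30) = 0.0775, z = 2.58, p = 0.005.
- FMT 4/30: p = 0.022.
- FMT 5/30: SE = 0.0873, z = 0.1333/0.0873 = 1.53, p = 0.063.

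In this example, two reclassified FMT subjects change the conclusion at 0.05. That is more than the 0.4 expected in step 6, so it shows how few subjects matter, not what is likely to happen.

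**8. Room for a delay.** Open-label entry runs from day 7 to day 21 after blinded treatment (14 − 7 to 14 + 7). A placebo subject unblinded on day 7 then needs the 7 days of antibiotics and 2 days of rest in Section 5.2.3: 7 + 7 + 2 = day 16, before day 21. An FMT subject goes straight to capsules and can enter from day 7.

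**The case against.** The strongest reply is that the documents do not put unblinding inside the event window. Several stronger readings are tempting, and the text does not support them.

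- **That unblinding is immediate.** Section 5.2.3 says only that it follows the dose. With entry up to day 21, it could follow the whole 7-day window. This stands, and it is why the exposure is a range.
- **That blinded judgement is impossible.** Section 6.1 asks for a blinded investigator, and Section 4.1.3 already separates blinded from unblinded nurses. A separate assessor is not ruled out, but none is provided for.
- **That every later event is compromised in the same way.** Open-label FMT is unblinded by design, so a blinded relatedness call there has little meaning. For that phase Section 6.1 needs only a limit on its scope.
- **That the team could deduce later assignments within a block.** Section 4.1.4 states neither a block size nor whether it is fixed, and no accrual rate is given. The inference has no basis in the documents.

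Two further replies carry some weight. The tested endpoint in Sections 7.1 and 7.3 does not use relatedness, so the bias there runs only through reporting and severity grading. And if the outcome were cut at the Week 8 visit, no counted event would follow unblinding. The plan does not state that cut, however, and Day 49 is seven weeks after the first dose, not eight.

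The Week 8 PUCAI is not at issue, since Section 5.2.2 has it completed before the visit.

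**Conclusion.** The concern holds as a gap in protection. The plan does not secure blinded judgement of severity, expectedness and relatedness for events in the 7 days after the last blinded dose, although Section 6.1 requires it and those events plausibly count toward the primary outcome. It does not follow that the judgement will in fact be unblinded.

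The size is modest: at most 12.5% of dose-weeks, falling to zero if release happens to come 7 or more days after the dose. The figure of 0.4 to 0.6 subjects per arm rests on an even spread of events. The whole point assumes that the outcome window extends past the Week 8 visit, as all three readings in step 3 of the check do. This is a change the sponsor should make because it is cheap and removes an avoidable source of bias; the trial's conclusions are not shown to depend on it.

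**What to change.** - **Section 5.2.3:** state that the assignment is released only after an AE contact about 7 days after the Week 8 dose, and only once all AE judgements for the blinded period are entered and locked.
- **Section 5.1:** add that contact to the schedule, before the unblinding column.
- **Sections 5.3.3, 7.1 and 7.3:** end the primary between-arm AE comparison at that contact. Later events are still collected and reported, outside that comparison.
- **Section 6.1:** limit the blinded-investigator rule to the same period.

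**Cost.** One telephone contact and up to 7 days' delay in unblinding. Subjects going into follow-up already have weekly contact in the first month, so the call is new mainly for those entering open label. The delay fits the stated 7 to 21 day entry window. If the sponsor reads that window as allowing entry before day 7, those earliest days would be lost.
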